10.4.3 Handling of missing values/censoring/discontinuations

During the dose-finding part of the trial, one additional patient may be enrolled in each cohort, for each patient who does not meet the criteria necessary for inclusion in the dose-determining set. During the dose expansion part of the trial, one additional patient may be enrolled for each patient who does not meet the criteria necessary for inclusion in the safety set. At the time of the writing of the study report, patients will have continuing events (e.g., adverse events) summarized using the data cut-off date as the date of completion, with an indication within the listings that the event is continuing.

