Phase I patients who complete a total of 6 cycles of combination therapy will be assessed for clinical response by IWG-MRT criteria. Patients who achieve at least Stable Disease (SD) by IWG-MRT (Table 4-1) can remain on therapy indefinitely or until disease progression or drug toxicity as assessed by the investigators in the Phase I extension stage. After 24 cycles, stable patients may be seen every other month at the discretion of the investigator. At the discretion of the investigator, phase I patients who have completed 6 cycles of therapy with a minimum of SD can also be dose escalated at that time to the RPTD once it is determined. These patients will not be considered for evaluation of response in Phase II.

Myelosuppression is expected and anticipated given the known toxicity profiles of these drugs in single agent therapy for MF. During the dose evaluation stage, Days 1-28, while both drugs are administered in combination, platelet transfusions will not be allowed to avoid the predetermined DLT of platelet count $<10 \times 10^9/L$ or any platelet count with grade 3 bleeding. If a platelet transfusion is indicated by best clinical practice guidelines and the PI feels it is necessary to transfuse a patient in these 28 days of the phase I study even at a platelet count $>10 \times 10^9/L$, then the patient will be transfused and will come off study and this will be considered a DLT. Platelet transfusions are allowed and should be given when clinically indicated and at the discretion of the investigator in Phase I continuation stage and extension stage. This would not necessarily require discontinuation from the study.

Phase II

Expansion stage [Cycles 1-6]

Once a RPTD is determined from the dose escalation phase I part of this trial, the dose expansion of the phase-II part of this trial will commence with 16 additional patients added to the 6 original RPTD cohort from phase I to total 22 patients. See Figure 4-1 B. IWG-MRT response criteria will be applied at the end of cycle 6 and this will include spleen volume measurement by MRI/CT and bone marrow biopsy to appreciate changes in morphology, degree of reticulin/collagen fibrosis, cytogenetics and molecular markers. Patients who have obtained at least SD by IWG-MRT can remain on study receiving combination therapy in the phase II extension stage.

Extension stage [Cycles 7+]

[figure not shown]

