6.2.5 Definitions of dose limiting toxicities (DLTs)

DLTs are listed in Table 6-3, and will be defined as all AEs of the specified grade occurring within Days 1-28 of the combination phase, unless clearly and incontrovertibly due to extraneous causes.. Table 6-3 was created using Common Terminology Criteria for Adverse Events (CTCAE) v4.03.

For the purpose of dose-escalation decisions, only DLTs occurring during the first 28 days of treatment with RUXOLITINIB and PANOBINOSTAT will be considered and included in dose escalation decisions. However, all safety information including adverse events, ECG monitoring data, and vital sign abnormalities, will be included in the final decision for dose escalation and determination of how many patients should be evaluated at a given dose level.

Thrombocytopenia will only be considered a DLT in the combination phase (Day 1-28) if the platelet count is recorded below 10,000/ μ l by manual count or $\geq 10,000/\mu\text{l}$ and associated with a grade 3 bleed. Phase I patients who require platelet transfusions within Days 1-28 will have to be removed from study. Patients are allowed to receive platelet transfusions after day 28 if clinically warranted, and this does not necessitate removal from study. Transfusional support of red blood cells (RBC) is permissible at any point in the study and is not considered a DLT.

In the event that an AE begins during the first 28 days of combination therapy, but does not qualify for the definition of a DLT at the time of the dose-escalation decision, due to a specific length requirement until Cycle 2; it will be provisionally considered a DLT during the decision-making process. Adverse events occurring after treatment day 28 will not be considered DLTs, however, they will guide the decision of dose escalation and how many patients will be evaluated at a given dose level. All AE's, vital signs, and ECG data will be included in the final analysis to determine the MTD and/or RPTD.

Table 6-3 Criteria for Defining Dose Limiting Toxicity (DLT)

TOXICITY	Any of the following criteria:
Hematologic	
Febrile Neutropenia	≥Grade 3 (ANC < 1.0 x 10 ⁹ /L + Fever single reading >38.3°C or ≥38°C sustained >1 hr)
Thrombocytopenia	<10 x 10 ⁹ /ul or ≥10 x 10 ⁹ /ul associated with grade 3 bleeding
Non-Hematologic	
Gastrointestinal	
Vomiting	≥Grade 3
Nausea	≥Grade 3 nausea uncontrolled despite use of standard anti-emetics
Diarrhea	≥Grade 3 Diarrhea
Constitutional symptoms	
Fatigue	Grade 4 Fatigue

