10.3 Treatments (study treatment, concomitant therapies, compliance)

The dose and duration in days of PANOBINOSTAT and RUXOLITINIB will be listed and summarized by dose level using descriptive statistics. Data may be presented by cycle in addition to over the entire study duration. The daily dose will be summarized using descriptive statistics by dose level and will be listed by patient.

Concomitant medications and significant non-drug therapies prior to and after the start of the study drug will be summarized for the safety set.

Compliance to the study protocol will be assessed by reporting the number and type of protocol deviations. These will be identified prior to database lock and will be listed and summarized.

In this trial, the days of each cycle will continue to be counted even if study drugs are being held. It will be the responsibility of the investigators to monitor the actual cumulative doses each patient is receiving per cycle.

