10.5 Secondary objectives

The secondary objectives of this study are:

10.5.1 To evaluate the safety of the oral co-administration of RUXOLITINIB and PANOBINOSTAT to patients with MF

All adverse events recorded during the study will be listed and summarized. All serious adverse events will be listed by patients and tabulated by type of adverse event and initial dose level. Any other safety information will be listed and tabulated as appropriate. This includes analysis of all AE, SAE, labs, vital signs, and ECG data to include dose level and cycle.

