10.5.2.2 Adverse events (AEs)

Summary tables for adverse events (AEs) will include only AEs that started or worsened during the on-treatment period, the **treatment-emergent** AEs. However, all safety data (including those from the pre and post-treatment periods) will be listed and those collected during the pre-treatment and post-treatment period will be flagged.

The incidence of treatment-emergent adverse events (new or worsening from baseline) will be summarized by system organ class, preferred term, severity (based on CTCAE grades), type of adverse event, relation to study treatment, and dose level. Deaths reportable as SAEs and non-fatal serious adverse events will be listed by patient and tabulated by type of adverse event and dose level.

Specific safety event categories (SEC) will be considered. Such categories consist of one or more well-defined safety events which are similar in nature and for which there is a specific

clinical interest in connection with the study treatment(s). For each specified SEC, number and percentage of patients with at least one event part of the SEC will be reported.

DLTs will be listed and their incidence summarized by primary system organ class, worst grade, type, and dose level. The dose determining set will be used for these summaries.

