10.5.2.3 Laboratory abnormalities

For laboratory tests covered by the Common Terminology Criteria for Adverse Events (CTCAE) version 4.03 (NCI 2009), the study's biostatistical and reporting team will grade laboratory data accordingly. For laboratory tests covered by CTCAE, a grade 0 will be assigned for all non-missing values not graded as 1 or higher. Grade 5 will not be used. For laboratory tests where grades are not defined by CTCAE, results will be graded by the low/normal/high classifications based on laboratory normal ranges. The following by-treatment summaries will be generated separately for hematology and biochemistry laboratory tests:

- frequency table for newly occurring on-treatment grades 3 or 4 (see below for details)
- shift tables using CTCAE grades to compare baseline to the worst on-treatment value
- for laboratory tests where CTCAE grades are not defined, shift tables using the low/normal/high/(low and high) classification to compare baseline to the worst on-treatment value.
- listing of all laboratory data with values flagged to show the corresponding CTCAE grades and the classifications relative to the laboratory normal ranges. Time to onset of grade 3 or higher SECs will be summarized by dose level.

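### Adverse events are summarised by dose level without allowing for unequal, open-ended follow-up, so comparisons beyond Cycle 1 can be distorted

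*Combined protocol and SAP*

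**What the plan says.** All references are to the combined protocol and SAP.

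- **Ongoing events (10.4.3).** For events that have not ended when the report is written, the rule is that "patients will have continuing events (e.g., adverse events) summarized using the data cut-off date as the date of completion". The listings are to mark such events as ongoing.
- **Incidence (10.5.2.2).** "The incidence of treatment-emergent adverse events (new or worsening from baseline) will be summarized by system organ class, preferred term, severity", and then by relation to treatment and dose level, among other factors. Under 10.5.2.1 the counting window runs from the first study dose until 30 days past the last one.
- **Time to onset (10.5.2.3).** "Time to onset of grade 3 or higher SECs will be summarized by dose level". No estimator or censoring rule is named.
- **Length of treatment (4.1).** After six cycles, Phase I patients with at least stable disease "can remain on therapy indefinitely or until disease progression or drug toxicity".
- **Entry of cohorts (10.4.2.1).** A cohort may begin combination therapy only once the previous cohort has finished its evaluation period.
- **Use of the data (6.2.5).** "All AE's, vital signs, and ECG data will be included in the final analysis to determine the MTD and/or RPTD". Sections 6.2.3 and 6.2.3.2 also bring tolerability after Cycle 1 into the choice of the RPTD.
- **Partial safeguards.** Section 10.5.1: "This includes analysis of all AE, SAE, labs, vital signs, and ECG data to include dose level and cycle". Section 10.3: "The dose and duration in days of PANOBINOSTAT and RUXOLITINIB will be listed and summarized by dose level using descriptive statistics".

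**The concern.** Sequential entry and open-ended treatment mean that early cohorts can be observed much longer than late ones. A crude percentage with at least one event rises with time on treatment. A difference between dose levels in such a table therefore mixes dose with length of observation. The section whose title includes censoring gives ongoing events a completion date instead of censoring them, so any summary of duration counts an unfinished event as finished. The more recent the cohort, the more its durations are cut.

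At stake is how the multi-cycle safety profile is read across dose levels. The protocol says that this profile contributes to the RPTD, and it is what a reader of the final report will use to judge dose and toxicity after Cycle 1.

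**Working it through.** **The plan's own safety figure.** Sections 10.4.2.2 and 10.8 give a 90% chance of seeing an AE with 10% incidence in 22 patients. The check is 1 − 0.9^22 = 0.9015, so it reproduces. The figure has no time attached: it holds if 10% is the incidence over the follow-up actually obtained.

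**Spread of follow-up.** Table 6-2 lists eight cohorts (1, 2, 3, 4a, 4b, 5, 6, 7) and the evaluation window is 28 days. If all open, the minimum gap between the first and last combination start is 7 × 28 = 196 days, or 7 cycles. When the last cohort has 6 cycles, a cohort 1 patient still on treatment has 6 + 7 = 13.

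**Effect on crude incidence.** Assumptions, not in the documents: constant hazard, nobody stops early, hazard ratio (HR) 1.5 for the more toxic dose. With p the six-cycle incidence at the safer dose, incidence after k cycles is 1 − (1 − p)^(k × HR / 6).

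| p | Safer dose, 13 cycles | More toxic dose, 6 cycles | Both at 6 cycles (safer vs more toxic) |
|---|---|---|---|
| 10% | 20.4% | 14.6% | 10% vs 14.6% |
| 20% | 38.3% | 28.4% | 20% vs 28.4% |
| 30% | 53.8% | 41.4% | 30% vs 41.4% |

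For p = 20%: 1 − 0.8^(13/6) = 0.383 and 1 − 0.8^1.5 = 0.284. The crude order is wrong in every row, and a common six-cycle window restores it. Under this model the order reverses whenever the hazard ratio is below the ratio of follow-up times, here 13/6 = 2.17.

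**A case where the order survives.** Suppose the report waits until Phase II patients have had six cycles. The last cohort then has at least 1 + 6 = 7 cycles and the first 14. Take a three-fold hazard and incidence 1 − exp(−hazard × cycles). Safer against more toxic dose is 50% vs 65% (0.05 per cycle at the safer dose), 75% vs 88% (0.10) and 94% vs 98.5% (0.20). The order is right, because 3 exceeds 14/7 = 2.

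**Timing from the protocol's own data.** Section 1.3.3 reports grade 3 or 4 thrombocytopenia in 40 of 154 patients (26.0%) on ruxolitinib alone, with 20% of the events in the first 4 weeks and 48% in the first 16. With that timing, 26.0% would read as 0.20 × 26.0 = 5.2% at week 4 and 0.48 × 26.0 = 12.5% at week 16. The 90% figure would become 1 − (1 − 0.020)^22 = 0.36 and 1 − (1 − 0.048)^22 = 0.66. More than half of these events came after week 16, so later cycles matter. The rate does fall, from 20/4 = 5% of events per week to (48 − 20)/12 = 2.3%, so a constant hazard is only a rough guide.

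**Effect on durations.** Section 6.2.7 expects worsening anemia to resolve in 4 to 6 months. Assume an exponential duration with median 150 days, hence mean 150/ln 2 = 216. With F days of follow-up after onset, closing events at cut-off gives median min(150, F) and mean 216 × (1 − exp(−F/216)).

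| F (days) | Median | Mean |
|---|---|---|
| 28 | 28 | 26 |
| 84 | 84 | 70 |
| 224 | 150 | 140 |

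The median recovers with long follow-up, but the mean remains below 216.

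**The case against.** The other side has real force.

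- **Escalation is protected.** DLTs are counted in the same 28-day window for every cohort, and the MTD follows from them. A reader might infer that unequal follow-up undermines dose escalation; the documents do not support that.
- **The completion-date rule is narrow.** It changes durations only, not incidence or time to onset. No AE-duration table is specified in 10.5, and the listings flag ongoing events. The rule still governs any duration summary that is produced.
- **Time to onset is unspecified, not wrong.** A reader might infer an uncensored analysis, but 10.5.2.3 simply names no method.
- **Later is not always higher.** Cohort 4a may use less panobinostat than cohort 3, and cohort 5 has the same 120 mg per cycle as cohorts 3 and 4b. Phase I patients may also move to the RPTD after six cycles. It would therefore go too far to say that later, higher-dose cohorts will look safer.
- **An extreme snapshot proves little.** Freezing the data when cohort 7 ends its first cycle (8 cycles against 1) gives a dramatic reversal, but 10.4.3 applies at the study report, when follow-up is longer.
- **Cycle and exposure are mentioned.** Sections 10.5.1 and 10.3 help, but they give no number at risk and no common window, and do not link exposure to event rates.
- **Cohorts are small.** With 3 to 6 patients each, any estimate is imprecise. That argues for modest reporting, not for comparing unequal windows.

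Nor do the documents say that the 10.5.2 tables themselves decide the RPTD, which the investigator sets from Phase I data. What is documented is that AEs beyond Cycle 1 contribute, with no stated way of putting dose levels on an equal footing.

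**Conclusion.** The point holds as a reporting weakness. The plan summarises AEs by dose level without accounting for unequal, open-ended follow-up, and it gives ongoing events a completion date, which understates durations. Beyond Cycle 1, comparisons of dose levels can be distorted. With a hazard ratio of 1.5 and 13 against 6 cycles they can reverse (38.3% at the safer dose, 28.4% at the other, from an assumed six-cycle incidence of 20%). With a three-fold hazard and 14 against 7 cycles they do not. These figures assume a constant hazard, no early discontinuation and all eight cohorts opened at the minimum interval. The actual size and direction depend on the cut-off, who stops and when, and the shape of the hazard. The 28-day DLT and MTD decisions stand untouched.

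**What to change.** - **10.5.2.2:** for each dose level, report AE incidence in common windows (Cycle 1; Cycles 1 to 6) with the number of patients entering each window, plus first events per patient-cycle at risk. Keep the crude whole-period table as supplementary.
- **10.4.3:** treat events ongoing at cut-off as right-censored in any duration summary, and report how many are ongoing.
- **10.5.2.3:** state that time to onset is estimated by Kaplan-Meier, censored at the end of the on-treatment period or at cut-off.

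The cost is SAP wording and a few extra tables. Event start and end dates (8.1.1) and treatment duration (10.3) are already collected, so no new data or patients are needed. Estimates will be imprecise in cohorts of 3 to 6, so pool dose levels where 10.5.2.1 allows tables by groups of dose levels.

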10.4.4 Supportive analyses

Additional supportive analyses may be conducted if appropriate.

10.5 Secondary objectives

The secondary objectives of this study are:

10.5.1 To evaluate the safety of the oral co-administration of RUXOLITINIB and PANOBINOSTAT to patients with MF

All adverse events recorded during the study will be listed and summarized. All serious adverse events will be listed by patients and tabulated by type of adverse event and initial dose level. Any other safety information will be listed and tabulated as appropriate. This includes analysis of all AE, SAE, labs, vital signs, and ECG data to include dose level and cycle.

10.5.2 Safety objectives

10.5.2.1 Analysis set and grouping for the analyses

For all safety analyses, the safety set will be used, except for summaries of DLTs, for which the dose determining set will be used in addition to the safety set. All listings will be presented by dose levels and all tables will be presented by dose level or groups of dose levels, as appropriate, based on the number of dose levels used and number of patients treated.

The overall observation period will be divided into three mutually exclusive segments:

- Pre-treatment period: from day of patient's informed consent to the day before first dose of study medication
- On-treatment period: from day of first dose of study medication to 30 days after last dose of study medication
- Post-treatment period: starting at day 31 after last dose of study medication.

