4.1 Description of study design

Phase I/II open label, single institution, study of induction RUXOLITINIB followed by concurrent administration of RUXOLITINIB and PANOBINOSTAT in a 3+3 cohort dose escalation schema in eligible patients with MF (see Figure 4-2). Screening for this study will have a window of 56 days and start on day -84 with signing of informed consent. See Figure 4-1 A and B. Eligible patients will begin induction phase therapy on day -28, receiving single agent RUXOLITINIB PO BID daily for 28 days. The dose of RUXOLITINIB in the induction cycle days -28 to 0 will be the same dose that the patient will receive in the assigned combination cycles. Patients who maintain a platelet count $\geq 50,000/\mu\text{L}$ at Day 1 will then receive concomitant PANOBINOSTAT PO TIW QOW or PO TIW QW depending on the cohort assignment. The induction phase of the Phase I study is not the evaluable phase I component and AEs that are noted in the induction phase will not constitute a dose limiting toxicity (DLT) and patients who do not maintain a platelet count $>50 \times 10^9/\text{L}$ will be removed and will not be able to continue onto the combination drug evaluable phase I period of 28 days and will not be counted in the evaluable phase I cohort for the purposes of dose escalation.

Phase I

The first 28 days of combination therapy will be the evaluable phase I portion of the study. Patients who do not experience a defined DLT in the dose evaluation stage of phase I can remain on study receiving combination drug therapy for a total of 6 cycles (cycles 2-6). See Figure 4-1 A. AEs will continue to be recorded on all patients (phase I and II) receiving combination therapy beyond the first cycle of the study. Dose escalation rules are based on the standard 3+3 design as shown in Figure 4-2.

Note that in this Phase I study, the initial cohort(s) will fix the dose of RUXOLITINIB and escalate the dose of PANOBINOSTAT. Thus, the first endpoint will be to find the MTD of PANOBINOSTAT associated with a fixed dose of 10 mg of RUXOLITINIB. At that point, the dose of PANOBINOSTAT will be fixed at the MTD just mentioned, and RUXOLITINIB will be escalated to 15 mg. The rules of the 3+3 design will govern whether 15 mg is an acceptable dose for RUXOLITINIB in combination with the MTD of PANOBINOSTAT. The rules of the 3+3 design will again be employed to decide on the frequency of administration of PANOBINOSTAT.

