6.1 Investigational treatment

The terms “investigational study drug(s)” or “study drug(s)” will refer to oral RUXOLITINIB (also known as INCB18424) tablets and oral PANOBINOSTAT (also known as LBH589) capsules and both drugs will be supplied by Incyte and Novartis, respectively, at no cost to the subjects.

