6.1.1 Dosing administration

RUXOLITINIB is administered orally BID everyday in a 28-day treatment cycle (Q4wk). Induction phase dose is 10 mg PO BID. In the combination phase, the starting dose of RUXOLITINIB is 10 mg and may be increased to 15mg PO BID. See [Table 6-1](#), [Table 6-2](#) for dose and treatment schedules.

PANOBINOSTAT is administered orally TIW, QOW, or QW in a 28-day cycle depending on the assigned cohort. Starting dose of PANOBINOSTAT is 10mg TIW QOW and may be increased to 20mg TIW QW depending on the assigned cohort. See [Table 6-1](#) for dose and treatment schedules.

Patients may take RUXOLITINIB and PANOBINOSTAT without regard to food. However, once the patient has made a choice (e.g., take drug after breakfast or at fasting), it is recommended that patient will follow the election choice consistently throughout the protocol.

On Day -28, the first dose of RUXOLITINIB only will be administered at the clinical site. First dose of PANOBINOSTAT will start on Cycle 1 Day 1 administered with the RUXOLITINIB morning dose at the clinical site. See [Table 6-2](#) for provisional escalating dose levels.

Table 6-1 Dose and treatment schedule

Study treatments	Pharmaceutical form and route of administration	Escalating Doses	Frequency and/or Regimen
RUXOLITINIB	Oral	10,15 mg	Twice daily, 28-day cycles
PANOBINOSTAT	Oral	10, 15 mg	Three times a week, every other week, 28-day cycles OR Three times a week, every week, 28 day cycle To be taken with the AM dose of RUXOLITINIB

Patients will self-administer RUXOLITINIB and PANOBINOSTAT as instructed as follows:

- RUXOLITINIB will be orally administered BID (approximately 12 hours apart: morning and evening)
- PANOBINOSTAT should be taken orally TIW (e.g. day 1, 3, and 5) at the same time on each day with the AM dose of RUXOLITINIB. Doses should be separated by a minimum of 30 hours within the week of dosing

- Dose may be taken with or without food
- Each dose of study drug should be taken with a glass of non-carbonated water (approximately 8 ounces/240ml). Patients should be instructed to swallow the capsules/tablets whole and not chew them.
- Patients must avoid grapefruits, grapefruit juice, pomegranate, starfruit, starfruit juice, Seville oranges and Seville orange juice during the entire study treatment period

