10.1 Analysis sets

10.1.1 Full Analysis Set

Patients who took at least one dose of study medication will define the full analysis set which will be the primary analysis set for the safety and efficacy assessments

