10.1.2 Safety Set

The Safety Set includes all patients who received at least one dose of study medication. For this study, the safety set and the full analysis set are identical.

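### Safety tables by combination dose level start at the first ruxolitinib-only dose, so they mix induction events and patients never given panobinostat with combination exposure

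*Combined protocol and SAP*

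**What the plan says.** Section 6.1 says that the study-drug terms "will refer to oral RUXOLITINIB (also known as INCB18424) tablets and oral PANOBINOSTAT (also known as LBH589) capsules", so both agents count. Section 6.1.1 then gives the order of dosing: "On Day -28, the first dose of RUXOLITINIB only will be administered at the clinical site", and "First dose of PANOBINOSTAT will start on Cycle 1 Day 1 administered with the RUXOLITINIB morning dose at the clinical site". Appendix 2 shows a ruxolitinib-alone period in Phase II as well.

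The analysis definitions follow the first dose of either agent:

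- Section 10.1.2: "The Safety Set includes all patients who received at least one dose of study medication". It adds that this set is identical to the full analysis set of Section 10.1.1.
- Section 10.5.2.1: "On-treatment period: from day of first dose of study medication to 30 days after last dose of study medication". Tables are laid out by dose level or groups of dose levels.
- Section 10.5.2.2: the adverse-event summaries count every event that starts or worsens in that period.
- Section 10.5.2.3: laboratory shifts run from baseline to the worst on-treatment value. The baseline visit is not stated.

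Dose level is assigned once eligibility is confirmed (Section 7.1.2.1), before induction. Under Section 4.1, patients who do not hold the required platelet count at Day 1 are removed before panobinostat. The same section says that "AEs that are noted in the induction phase will not constitute a dose limiting toxicity". For the expansion, Section 10.4.3 provides that "one additional patient may be enrolled for each patient who does not meet the criteria necessary for inclusion in the safety set". Section 7.1.5.2 otherwise rules out replacing withdrawn patients, apart from an exception in Phase I Cycle 1.

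**The concern.** A reader of a table headed by a combination dose level will take the column as experience with that combination. Under these definitions the column also holds 28 days of ruxolitinib alone and some patients who never took panobinostat. The plan defines no induction period, no induction column and no combination-treated set. Section 4.1 keeps induction toxicity out of the DLT count, but that protection does not extend to the adverse-event incidence tables, the laboratory shifts or the time to onset of grade 3 or higher safety event categories.

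The event most exposed is thrombocytopenia, which Section 1.4.2 names as the main overlapping toxicity and Section 8.1.3 lists as of special interest. The tables matter beyond description because Sections 6.2.3 and 6.2.3.2 let the wider toxicity and tolerability profile inform the choice of RPTD.

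Replacement is a second gap. An expansion patient lost during induction is inside the safety set and so is not replaced, yet Section 10.4.2.2 bases its 90% detection statement on 22 patients treated at the MTD or RPTD.

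**Working it through.** **1. The plan's own figure.** Sections 10.4.2.2 and 10.8 give a 90% chance of detecting an adverse event of 10% incidence in 22 patients. Reading detection as at least one case: 1 − 0.9^22 = 0.9015. The figure is reproduced, and it requires all 22 to be exposed to the combination.

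**2. Induction events in the numerator.** Section 1.3.3 reports grade 3 or 4 platelet declines in 40 of 154 patients on ruxolitinib alone (31 grade 3 and 9 grade 4 events), with 20% of these events in the first 4 weeks.

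- All doses: 0.20 × 40/154 = 5.2% per patient, or 22 × 0.052 = 1.1 expected events in 22 patients.
- Started at 10 mg BID: 0.20 × 6/30 = 4.0%, or 0.9 in 22.
- Started at 15 mg BID: 0.20 × 1/35 = 0.6%, or 0.1 in 22.

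The two dose-specific lines assume the same 20% early share, which the protocol does not report by dose. As an illustration, take a 10% combination-period rate that is independent of induction. The tabulated rate with everyone exposed would be 1 − (1 − 0.052)(1 − 0.10) = 14.7%.

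**3. Never-exposed patients in the denominator.** If k of 22 never receive panobinostat, a true 10% rate of a panobinostat-related event is reported as 0.10 × (22 − k)/22:

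| k | Reported rate |
|---|---|
| 1 | 9.5% |
| 2 | 9.1% |
| 3 | 8.6% |

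This error runs opposite to step 2, so the net direction depends on the event.

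**4. Patients at risk of loss in the expansion.** Six of the 22 are carried forward from Phase I (Sections 10.4.2.2 and 10.8). As evaluable patients they have already entered combination treatment (Section 6.2.3). Only the 16 added patients can be lost in induction.

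The documents give no induction-failure rate. The range below is an assumption. Its lower end uses the 4.0% from step 2 as a stand-in for failing the Day 1 platelet criterion, and its upper end is 20%.

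| Assumed loss among 16 | Expected number exposed | Chance of at least one case of a 10% event |
|---|---|---|
| 0% | 22 | 1 − 0.9^22 = 90.2% |
| 4% | 22 − 0.64 = 21.36 | 1 − 0.9^21.36 = 89.5% |
| 10% | 22 − 1.6 = 20.4 | 1 − 0.9^20.4 = 88.3% |
| 20% | 22 − 3.2 = 18.8 | 1 − 0.9^18.8 = 86.2% |

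For whole numbers exposed, the chance is 89.1% with 21, 87.8% with 20 and 86.5% with 19.

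**The case against.** Counting safety from the first dose of any study drug is conventional and inclusive, and induction is part of the regimen under study. That is a good reason to keep the all-dosed set, but not to leave the combination period without a table of its own.

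The plan also offers some separation. Section 10.5.1 asks for safety data by dose level and cycle, and Section 4.1 calls induction a cycle. Section 10.5.2.2 tabulates by relation to treatment, and Section 8.2.2 asks for each SAE's relation to each agent. This is partial mitigation: the incidence tables in Section 10.5.2.2 do not list cycle, and a by-cycle split leaves the denominator unchanged.

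The terminology is also inconsistent. The analysis sections speak of study medication, while Section 6.1 defines study drug. Section 7.2.5.6 places the first dose of study drug on Cycle 1 Day 1, and Section 7.1.3 says that a run-in does not apply. Section 6.1 with Section 6.1.1 supports the Day -28 reading, but the conflict is real.

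A reader might infer that dose escalation or the MTD is contaminated. The documents do not support that. DLTs are confined to combination Days 1 to 28 (Section 6.2.5), patients who fail the platelet criterion are not counted for escalation (Section 4.1), and the MTD rests on the dose-determining set (Section 10.1.4). Section 10.4.1 makes DLT rates and the MTD or RPTD the quantities of primary interest.

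**Conclusion.** The point holds for the descriptive safety tables and for the number exposed in the expansion. Followed as written, the plan attributes single-agent events and never-exposed patients to a combination dose level. The expected contamination is about 5.2% of patients with a grade 3/4 platelet decline in induction, 4.0% at 10 mg BID and 0.6% at 15 mg BID, assuming that the earlier study's timing carries over. This trial's platelet entry limit of 75 × 10^9/L (Section 5.2) could make the rate higher.

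Attribution is the main defect. The loss of detection probability is secondary: 89.5% to 86.2% against 90.2%, on an assumed 4% to 20% loss among the 16 added patients.

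Two further readings go too far. One is that all 22 are at risk of induction loss, but the six carried forward have already passed that point. The other is that the tables must overstate combination toxicity, but the numerator and denominator errors pull in opposite directions.

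**What to change.** - In Section 10.5.2.1, split the on-treatment period into induction (first ruxolitinib dose to the day before first panobinostat) and combination (first panobinostat dose to 30 days after last dose). State the baseline for each.
- Tabulate adverse events and laboratory shifts for each period. Use a combination-treated safety set, defined by at least one panobinostat dose, as the denominator of the combination tables. Keep the all-dosed safety set alongside.
- Either tie the expansion replacement rule in Section 10.4.3, and the matching text in Section 7.1.5.2, to the combination-treated set, or restate the 90% for the number actually exposed.
- Keep the full analysis set of Section 10.1.1 as primary for response. Restricting response to panobinostat recipients would drop early failures and could inflate the response rate.
- Reconcile Sections 7.2.5.6 and 7.1.3 with Section 6.1.1 on when the first dose of study drug occurs, and define study medication.

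The cost is SAP wording, one extra set of tables and, if the replacement option is chosen, possibly a few more patients.
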